7 ASSESSMENTS

Every effort should be made to ensure that protocol-required tests and procedures are completed as described. However, it is anticipated that from time to time there may be circumstances, outside the control of the investigator that may make it unfeasible to perform the test. In these cases, the investigator must take all steps necessary to ensure the safety and well-being of the subject. When a protocol-required test cannot be performed, the investigator will document the reason for the missed test and any corrective and preventative actions that he or she has taken to ensure that required processes are adhered to as soon as possible. The subject should continue in the study as long as the safety of the subject is not compromised. The study team must be informed of these incidents in a timely manner.

7.1 Screening

The following assessments will be performed at times defined in the [Study Procedures](#) section of this protocol.

7.1.1 Informed Consent

The investigator, or designee, must obtain written (signed and dated by the subject) informed consent from each subject participating in this study after adequate explanation of the aims, methods, objectives, and potential hazards of the study. The investigator, or designee, must also explain to the subjects that they are completely free to refuse to enter the study or to withdraw from it at any time. Appropriate forms for documenting a written consent will be provided by the investigator or by GSK CH. The investigator, or designee, should sign and date the consent form to confirm that the consent process was completed correctly. The subject, will be provided with a copy of their signed and dated consent form and any other written information which they should be instructed to retain. If, during a subject's participation in the study, any new information becomes available that may affect the subject's willingness to participate in the study, each ongoing subject should receive a copy of this new information and be re-consented into the study. Subjects will be provided with a

 GlaxoSmithKline	Document Name	208397 Clinical Protocol 2.docx	Document Identifier	Effective Date
	Type	Version		
	eldo_controlled	2.0; Most-Recent; Effective; CURRENT	090032d580db1b91	24-Oct-2017 08:49:05
	Reason For Issue	Auto Issue		

Sodium-calcium mixed partial salt of poly(methylvinylether/maleic acid) and carboxymethylcellulose

208397

Final Clinical Protocol, 20 Oct 2017

copy of the signed and dated amended consent form. The date of consent will be recorded on the CRF.

7.1.2 Dental History

The Investigator, or medically qualified designee, will take a dental history from each subject. Dental history will include information of all prostheses in the mouth, maxillary and mandibular, as well as information regarding the age of the dentures, how long the subject has worn dentures, the prosthetic teeth material and whether the subject is a regular user of denture adhesives.

7.1.3 Well-Fit Assessment, Kapur (Olshan Modification) Index

Each denture (upper and lower) will be examined for retention and stability using the Kapur Index (Olshan Modification) ([Kapur, 1967](#); [Olshan, 1992](#)) by an examiner with expert knowledge of prosthodontics. A sum score (upper + lower) of ≥ 6 is required for inclusion.

Retention:

With gloved hands, the examiner will attempt to unseat the upper and lower denture by applying an opposing vertical force at the canine/lateral incisor region of the denture. The examiner will score retention as 0 - 5 using the following criteria:

5= Excellent- denture offers excellent resistance to vertical pull and lateral force.

4= Very Good- denture offers very good resistance to vertical pull and lateral force.

3= Good- denture offers moderate resistance to vertical pull and lateral force.

2= Fair- denture offers moderate resistance to vertical pull and little or no resistance to lateral forces.

1= Poor- denture offers slight resistance to vertical pull and little or no resistance to lateral force.

0= No retention- when the denture is seated in place, it displaces itself.

Stability:

With gloved hands, the examiner will attempt to rock the seated dentures by placing alternate horizontal force at the cuspid and contralateral molar regions of the upper and lower dentures.

The examiner will score denture stability as 0 - 4 using the following criteria:

4= Excellent- when denture base offers no rocking on its supporting structures under pressure.

3= Good- when denture base has very slight rocking on its supporting structures under pressure.

2= Fair- when denture base has slight rocking on its supporting structures under pressure.

1= Poor- when denture base has moderate rocking on its supporting structures under pressure.

0= No stability- when denture base has extreme rocking under pressure.

Sum score (upper + lower denture) of <6 = dentures with poor retention and stability.

 GlaxoSmithKline	Document Name	208397 Clinical Protocol 2.docx		
	Type	Version	Document Identifier	Effective Date
	eldo_controlled	2.0; Most Recent; Effective; CURRENT	090032d580db1b91	24-Oct-2017 08:49:05
	Reason For Issue	Auto Issue		

Sodium-calcium mixed partial salt of poly(methylvinylether/maleic acid) and carboxymethylcellulose

208397

Final Clinical Protocol, 20 Oct 2017

Sum score (upper + lower denture) 6-9 = dentures with fair retention and stability.

Sum score (upper + lower denture) 10-14 = dentures with good retention and stability.

Sum score (upper + lower denture) >14 = dentures with very good retention and stability.

Subject recruitment will be controlled to ensure 50±10% of the subjects will be in each of the low and high Kapur-Olshan groups [the low Kapur-Olshan group is defined as a composite Kapur-Olshan score of 6-14 (clinically fair and good dentures) and the high Kapur-Olshan score as 15-18 (clinically very good dentures)].

7.1.4 Well Made Assessment

Clinical Acceptability

Each denture (upper and lower) will be examined. Only dentures having adequate (as judged by an examiner with expert knowledge of prosthodontics) vertical dimension, freeway space, horizontal occlusal relationships and border extension will be considered clinically acceptable. For each denture (upper and lower), the examiner will indicate acceptable or unacceptable on the CRF.

Denture Finish and Contour

The contour and finish of each denture (maxillary and mandibular) will be examined. Only dentures with acceptable (as judged by an examiner with expert knowledge of prosthodontics) porosity, tissue surfaces, polished surfaces, colour and thickness will be accepted. For each denture (upper and lower), the examiner will indicate acceptable or unacceptable on the CRF.

7.1.5 Food Migration Adequacy Determination

Subjects must complete the food migration adequacy assessment whilst using no denture adhesives/fixatives. Dentures should have been cleaned and dried by the study staff and replaced in the subject's mouth. Subjects will be provided with 30-32 grams (accurately weighed) of non-salted peanuts, divided into smaller portions of approximately eight peanut halves by the study staff. Each portion should be chewed by the subject for approximately 20 seconds, after which the subject will be instructed to swallow at anytime they are comfortable. Subjects will be allowed small sips of water during the peanut consumption to aid chewing as appropriate. After completion of the peanut consumption, the subject will rinse their mouth with water for five seconds before removing their denture. Subjects will be asked to remove their dentures (the examiner may assist in this if required) and place them into a labelled tray (with subject screening number) teeth side down, and may remove any residual peanut particles from their mouth with water and a gauze pad (not for collection). The amount of food particles on each denture will be visually assessed by the examiner according to the scale below and recorded in the CRF to determine if there is evidence of peanut particle migration under the dentures. The following 0 – 3 assessment scale will be used. Subjects who present no evidence of peanut particles under either the upper or lower denture (i.e. if either denture scores as 0) will not be eligible.

The location and extent of peanut particle migration will be rated as follows:

GlaxoSmithKline Consumer Healthcare Confidential

Template Version Effective: 22-Jun-2017

Page 32 of 62

 GlaxoSmithKline	Document Name	208397 Clinical Protocol 2.docx		
	Type	Version	Document Identifier	Effective Date
	eldo_controlled	2.0; Most Recent; Effective; CURRENT	090032d580db1b91	24-Oct-2017 08:49:05
	Reason For Issue	Auto Issue		

Sodium-calcium mixed partial salt of poly(methylvinylether/maleic acid) and carboxymethylcellulose

208397

Final Clinical Protocol, 20 Oct 2017

0= None – No peanut migration under the denture.

1= Minimal – Slight migration of peanuts under the denture.

2= Moderate – Migration of peanuts over the internal walls of the denture.

3= Extensive – Peanuts migration on the crest of the denture.

Dentures should be cleaned thoroughly by the study staff prior to returning to the subject.

7.2 Efficacy

The following efficacy assessments will be performed at times defined in the [Study Procedures](#) section of this protocol.

7.2.1 Food Occlusion Testing Incorporating Denture Dislodgement Assessment

Food Occlusion will be measured by a trained or experienced operator using the method described below. 60 ± 5 minutes after the dentures have been inserted:

1. The subject will be instructed to bite down firmly on their dentures. The subject will then briefly rinse their mouth vigorously with water. The site staff will remove any adhesive that is oozing from the dentures. Note: The subject must not eat any food during the 60 ± 5 minutes waiting period. Subjects may not drink during this 60 ± 5 minutes period with the exception of small sips water.
2. The subject will be given 30-32g of non-salted, dry roasted peanuts to chew and swallow. The 32g portion of peanuts will be divided by the site staff in to smaller portions of approximately 8 peanut halves (approximately 4g). The subject will be asked to chew each pre-measured portion of peanuts for at least 20 seconds, after which they may swallow at any time they are comfortable. The subject may sip water during peanut consumption.
3. Whilst consuming the peanuts the subject should note the number of times they experience their denture dislodging. The total number of denture dislodgements for the subject should be recorded by the study site staff in the CRF.
4. After consuming all of the peanuts, the subject will rinse their mouth with water for approximately 5 seconds (to remove any peanut particles not retained under the dentures).
5. The examiner will carefully remove the subject's lower denture and place it on a small tray, teeth side down and remove any residual adhesive and/or peanut particles from the lower gum with a piece of gauze that will be placed in a separate beaker coded with the subject screening number, treatment period and "L" for lower denture.
6. The examiner will carefully remove the subject's upper denture and place it on a small tray, teeth side down and remove any residual adhesive and/or peanut particles from the roof of the mouth with a piece of gauze that will be placed in a separate beaker coded with the subject screening number, treatment period and "U" for upper denture.

 GlaxoSmithKline	Document Name	208397 Clinical Protocol 2.docx	Document Identifier	Effective Date
	Type	Version		
	eldo_controlled	2.0; Most Recent; Effective; CURRENT	090032d580db1b91	24-Oct-2017 08:49:05
	Reason For Issue	Auto Issue		

Sodium-calcium mixed partial salt of poly(methylvinylether/maleic acid) and carboxymethylcellulose

208397

Final Clinical Protocol, 20 Oct 2017

7. All the surfaces of the dentures will be checked for residual peanuts. If any is found on any surface other than those in contact with oral soft tissue, it will be removed with a spatula and discarded.
8. For a subset of approximately 5 subjects at each treatment visit, a photograph of the fit surface of the dentures will be taken as per section 7.2.3.
9. The upper and lower dentures of each subject will be placed in the coded beakers with the gauze (upper and lower separately).
10. Immediately following removal of the prostheses the subject will complete the study questionnaire per section 7.2.2.
11. In the laboratory, approximately 100 ml (or enough to cover the prostheses) of hot de-ionised water (90 °C, (194 °F)) will be added to each beaker. The beakers will be sonicated for 30 minutes to loosen any adhering peanut particles.
12. After sonication, any peanut particles still remaining on the prostheses or the gauze will be washed out into the beaker. The gauze pieces will be discarded and the dentures will be cleaned and returned to the subject.
13. The dentures should be cleaned thoroughly before returning to the subject.
14. The solutions in the beakers (mixture of water, adhesive, saliva and peanut particles) will be heated to boiling with frequent stirring to dissolve any undissolved adhesive.
15. The hot solution in each beaker will be strained through a standard testing sieve, USA #60 (coded with subject's screening number, treatment code and U or L for upper and lower dentures).
16. The residue remaining on the screen will be washed repeatedly with hot water to remove any adhesive or saliva.
17. The collected peanut particles will be air-dried overnight on the screen.
18. The dried particles will be transferred from the screen to pre-weighed coded (subject screening number, Upper/Lower and date) aluminium weighing pans using a spatula and then will be dried in an oven at 40°C (105°F) for 5 hours.
19. The pans will be removed from the oven, cooled to room temperature and then weighed (in grams, to 4 decimal places) to determine the mass of the particles collected from each denture.

Prior to commencing this testing the subjects will have the entire food occlusion and denture dislodgement assessment procedure explained to them at each visit by the examiner or a designee. A standard script will be used to ensure consistency in procedures.

Document Name	208397 Clinical Protocol 2.docx	Document Identifier	Effective Date
Type	Version		
eldo_controlled	2.0; Most Recent; Effective; CURRENT	090032d580db1b91	24-Oct-2017 08:49:05

Sodium-calcium mixed partial salt of poly(methylvinylether/maleic acid) and carboxymethylcellulose

208397

Final Clinical Protocol, 20 Oct 2017

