On each test day (Visits 2-4) subjects will undergo an OST examination and have their dentures cleaned. Treatment (or no treatment as per the randomisation schedule) will then be applied as per the application instructions and the dentures worn by the subject. Then, 60±5 minutes after inserting their dentures each subject will be given a standardised portion of peanuts to consume, following a prescribed chewing and swallowing method. Whilst chewing the peanuts subjects will record the number of denture dislodgements that occur during the chewing procedure. After this, subjects will rinse their mouth with water. The examiner will then remove the lower denture and any peanut particles or adhesive remaining on the mandibular ridge will be removed using gauze. The examiner will then remove the upper denture and any peanut particles or adhesive remaining on the palate will be removed using new gauze. The subject will then complete a questionnaire on efficacy and a further OST examination will be performed.

For a subset of subjects the fit surface of their dentures will be photographed before peanuts are collected from the fit surface. These subjects will be selected at the discretion of the Investigator, but allow for a variety of denture sizes and fit to be represented. It is expected that approximately 5 sets of dentures be photographed per treatment group, and where possible that consistency of subjects between treatments is maintained (i.e. a subject will be identified at visit 2 as being suitable for denture imaging and will have their dentures

Document Name	208397 Clinical Protocol 2.docx	Document Identifier	Effective Date
Type	Version		
eldo_controlled	2.0; Most-Recent; Effective; CURRENT	090032d580db1b91	24-Oct-2017 08:49:05

Sodium-calcium mixed partial salt of poly(methylvinylether/maleic acid) and carboxymethylcellulose

208397

Final Clinical Protocol, 20 Oct 2017

photographed at visits 2, 3 and 4 however, should subject dropouts or other reasons necessitate, subjects can be substituted).

Peanut particles will then be collected from the fit surfaces of the dentures and the gauzes and weighed to evaluate the mass of food particles that had migrated under the denture (keeping the particles associated with the upper and lower dentures separate).

These procedures will be repeated in a crossover manner. There will be between 2-30 days between treatment visits to allow for recovery from the mastication procedures.

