7.2.2 Subject Questionnaire

After the food occlusion testing and following removal of the dentures on Test Days, the subject will complete a questionnaire ([Section 13.2](#)) on their experience during the chewing procedure. The subject responses should be transcribed by the study staff to the CRF. The study staff should be mindful that whilst the questionnaire does not solicit safety information, any information on safety outcomes recorded by subjects on the questionnaire should be evaluated by the investigator to ensure all AEs are recorded.

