13.2 Subject Completed Questionnaire

The following questions are about the peanut chewing you have just undertaken. Thinking about **only the peanuts you have just chewed** please circle one answer for each question.

1) Were you aware of peanuts under your denture? (Please circle your answer)

Yes

No

Only answer questions 2-4 if you circled "Yes" for question 1 above.

2) On a scale of 1 to 10 how would you rate the **amount** of peanut particles that went under your denture? (Please circle your answer)

1 2 3 4 5 6 7 8 9 10

None

Numerous

3) On a scale of 1 to 10 how would you rate the **irritation** of peanuts under your denture? (Please circle your answer)

1 2 3 4 5 6 7 8 9 10

Not at all Irritating

Extremely Irritating

4) On a scale of 1 to 10 how **bothered** were you by the peanuts that went under your denture? (Please circle your answer)

1 2 3 4 5 6 7 8 9 10

Not at all Bothered

Extremely Bothered

Document Name	208397 Clinical Protocol 2.docx	Document Identifier	Effective Date
Type	Version		
eldo_controlled	2.0; Most-Recent; Effective; CURRENT	090032d580db1b91	24-Oct-2017 08:49:05

Sodium-calcium mixed partial salt of poly(methylvinylether/maleic acid) and carboxymethylcellulose

208397

Final Clinical Protocol, 20 Oct 2017

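### The questionnaire on what subjects noticed while chewing is completed after the dentures are out, and nothing keeps dentures, gauze or beakers out of their sight

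*Protocol*

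**What the plan says.** Protocol 7.2.1 lists the test procedure in numbered steps. Dislodgements are noted during chewing (step 3), and the subject then rinses (step 4). For the lower denture, step 5 reads "The examiner will carefully remove the subject's lower denture and place it on a small tray, teeth side down"; for the upper, step 6 reads "The examiner will carefully remove the subject's upper denture and place it on a small tray, teeth side down". In both steps the examiner also wipes the tissue with gauze. Surfaces are checked (step 7), a subset is photographed (step 8), dentures and gauze go into beakers (step 9), and step 10 says: "Immediately following removal of the prostheses the subject will complete the study questionnaire per section 7.2.2".

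Other sections also put the form after removal. Protocol 7.2.2 opens with "After the food occlusion testing and following removal of the dentures on Test Days, the subject will complete a questionnaire". Protocol section 3, after describing removal of both dentures and the gauze, continues "The subject will then complete a questionnaire on efficacy and a further OST examination will be performed", and SAP 1.1 gives the same order.

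The form (Protocol 13.2) begins with "Were you aware of peanuts under your denture", answered Yes or No. Only those who circle Yes go on to rate amount, irritation and bother from 1 to 10. Protocol 7.2.2 says the form concerns the subject's experience while chewing. Protocol 1.2.1 says the questionnaire and dislodgement data will support the peanut mass findings.

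**The concern.** The form is meant to record what the subject felt with the dentures in place. At the time it is completed, the evidence of what went under the dentures has been brought into the open. A subject who noticed nothing while chewing, but then sees particles, can circle Yes and rate the amount by eye.

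At stake is the supporting role that section 1.2.1 gives these data. If questions 1 and 2 partly reflect visible residue, some of their agreement with the weighed mass comes from the procedure and says less about what subjects felt. In a method development study, whether the subjective measure adds separate information is itself worth knowing.

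**Working it through.** No arithmetic decides this point, and the plan states no figure to reproduce. The check sets the passages side by side.

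**1. Is the form always after removal?**

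| Source | Where the questionnaire falls |
|---|---|
| Protocol section 3; SAP 1.1 | After both dentures are out and both tissues wiped |
| Protocol 7.2.1 | Step 10; removal is steps 5 and 6 |
| Protocol 7.2.2 | After testing and after removal |
| Protocol 6.1.2 to 6.1.4 | After food occlusion testing, before photographs; removal not listed separately |

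Every source that fixes the order relative to removal puts the form after it. The visit lists do not contradict this.

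**2. Where are the dentures when the subject answers?** In strict step order they are already in beakers (step 9 precedes step 10). But step 10 ties the form to the moment of removal, and the visit lists put it before photography. Photography is step 8, so it comes before the beakers. On that reading, the dentures of photographed subjects are not yet in beakers when the form is completed. The exact moment is ambiguous.

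**3. Is the fit surface exposed?** The documents do not say so in words, but it follows from laying a denture teeth side down. Trapped particles sit on that surface.

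**4. Does anything prevent a view?** No section mentions a cover, a screen or opaque beakers, or tells the subject to answer before looking. The dislodgement count does not share the problem, because it is noted during chewing.

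**5. How would a cue reach the tables?** Let N be the subjects in a treatment group, a those aware by feel, and c those who answer Yes only because of what they see. Then:

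- Question 1 is reported as (a + c)/N instead of a/N.
- SAP Table 14.2.4 bases the percentages for questions 2 to 4 on aware subjects, so their denominator becomes a + c instead of a.

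The documents give no value for c, and it may be zero.

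**6. How many forms?** 48 subjects × 3 periods = 144 planned, or 50 × 3 = 150 at maximum enrolment. These are counts of forms completed under this procedure. They are not estimates of how many answers are cued.

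**The case against.** The strongest reply is that visibility is inferred. At treatment visits the examiner removes the dentures, and nothing says where the tray stands or that the subject looks at it. The standard script mentioned at the end of 7.2.1 is not in the documents. If the list is followed literally, the dentures are in beakers with the gauze by step 10. All of this stands, and it limits the point to what can happen. It does not remove it: the subject may have seen the tray during steps 5 to 8, and the beakers are not described as hidden.

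The form also tells subjects to think only of the peanuts just chewed, and question 1 is in the past tense. That sets the time frame and may reduce cueing, but it does not exclude it.

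A reader might infer three stronger things that the documents do not support:

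- **That all 144 forms are affected.** That is the planned number, and nothing shows how many answers would change.
- **That questions 1 and 2 are simply a second, visual reading of the mass endpoint.** The mass includes particles wiped from gum and palate, and is sieved, dried and weighed to four decimal places of a gram. A 1 to 10 impression is a different measurement.
- **That screening the dentures would make the questionnaire independent evidence of felt benefit.** The study is open label by stated choice (Protocol 1.2.1 and 5.1). Subjects know which visit had no adhesive and could see the dentures once the form is done. At screening they may already have seen their own dentures after chewing without adhesive (Protocol 7.1.5). A cover cures none of this.

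**Conclusion.** The point holds in a limited form. The questionnaire follows denture removal, its exact place relative to the beakers and photographs is unclear, and no section keeps dentures, gauze or beakers out of view. Sight can therefore cue questions 1 and 2 and, through question 1, alter who answers questions 2 to 4. This weakens their use as separate support for the mass result.

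The conclusion assumes that some subjects can see the dentures or gauze before answering, which the documents neither state nor prevent. The size is not estimable. The endpoint is exploratory and summarised descriptively (SAP 4.5.2), the study has no formal success criterion, and the primary mass endpoint, mixed model and safety analyses are unaffected. This is a cheap improvement to an exploratory measure and does not threaten the study's main result.

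**What to change.** In Protocol 7.2.1, choose one of two orders and state it:

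- the subject completes the questionnaire after the step 4 rinse and before either denture is removed; or
- the subject completes it after removal, with dentures, gauze and beakers covered or screened until the form is finished.

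Then align Protocol section 3, the visit lists in 6.1.2 to 6.1.4, 7.2.2, SAP 1.1 and the standard script, so that questionnaire, photography and beakers appear in one order throughout.

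The cost is a tray cover, or a short delay before removal if the form comes first. No extra staff are needed, and recovery and weighing do not change. Cueing cannot be removed from the answers once they are collected, so the change belongs before the first treatment visit.
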